APPENDIX 3. ACCEPTABLE BENZODIAZEPINES FOR CONCOMITANT USE

Benzodiazepine Equivalency

	Approximately Equivalent Oral Dose, mg	Time to Peak Level, hours	Half-life, hours
Alprazolam (Xanax)	≤1	1-2	12
Bromazepam (Lexotan)	≤6	1-4	20
Chlordiazepoxide (Librium)	≤25	1-4	100
Clonazepam (Klonopin)	≤0.5	1-4	34
Clorazepate (Tranxene)	≤15	0.5-2	100
Diazepam (Valium)	≤10	1-2	100
Flurazepam (Dalmane)	≤30	0.5-1	100
Lorazepam (Ativan)	≤2	1-4	15
Nitrazepam (Mogadon)	≤10	0.5-2	30
Oxazepam (Serax)	≤30	1-4	8
Quazepam (Doral)	≤20	1.5	25-41
Temazepam (Restoril)	≤20	2-3	11
Triazolam (Halcion)	≤0.5	1-2	2

Adapted from: Farinde A. Benzodiazepine Equivalency Table 2018 [cited 2018 December 20]. Available from: <https://emedicine.medscape.com/article/2172250-overview> (Farinde 2018)

MedDRA	Medical Dictionary for Regulatory Activities
mg	milligrams
██████	████████████████████
PK	pharmacokinetic
PS	performance subscale
PT	preferred term
QAM	every morning
RBC	red blood cell
SAE	serious adverse event
SAP	Statistical Analysis Plan
SD	standard deviation
SoA	Schedule of Activities
SOC	system organ class
$t_{1/2}$	apparent terminal elimination half-life
TEAE	treatment-emergent adverse event
TETRAS	The Essential Tremor Rating Assessment Scale
T_{max}	time to maximum observed concentration
ULN	upper limit of normal
Vd/F	apparent volume of distribution after non-intravenous administration
WBC	white blood cell

1 OVERVIEW

This Statistical Analysis Plan (SAP) describes the planned analysis and reporting for Protocol PRAX-944-221 (A Phase 2 Clinical Trial Evaluating the Efficacy, Safety, Tolerability, and Pharmacokinetics of PRAX-944 in Adults with Essential Tremor), Final Version 6.0 dated 11 August 2021.

The statistical analyses and summaries described in this SAP will follow the International Conference on Harmonization of Technical Requirements for Registration of Pharmaceuticals for Human Use (ICH) guideline for Statistical Principles for Clinical Trials (ICH E9 Expert Working Group, 1999) and will form the basis of the results sections of the clinical study report (CSR) in accordance with the ICH guideline for Structure and Content of Clinical Study Reports (ICH Harmonised Tripartite Guideline E3, 1995). This SAP will be finalized and fully executed before database lock and unblinding of treatment codes. Any changes to the analyses that are not included in this SAP will be documented in the CSR.

2 STUDY DETAILS

2.1 Study Objectives

A list of the specific protocol objectives for each study part along with their respective endpoints are listed in the tables below:

Part A

Objective	Endpoint
Primary	
To evaluate the efficacy of PRAX-944 on upper limb tremor in participants with ET	
 Change from Baseline to Day 7 and Day 14 in The Essential Tremor Rating Assessment Scale (TETRAS) upper limb score (bilateral sum of items 4a, 4b, and 4c)
Secondary	
To evaluate the efficacy of PRAX-944 on other measures of tremor severity in participants with ET	
 Change from Baseline to Day 7 and Day 14 in: TETRAS performance subscale total score Accelerometer-based upper limb score (bilateral sum of items 4a, 4b, and 4c) TETRAS performance subscale individual item scores
To evaluate the safety and tolerability of PRAX-944 in participants with ET	
 Incidence and severity of adverse events (AEs) Changes in vital sign measurements Changes in clinical laboratory results Changes in electrocardiogram (ECG) parameters Incidence of Columbia-Suicide Severity Rating Scale (C-SSRS) measured suicidal ideation or behavior

Exploratory

Part B

Objective	Endpoint
Primary	
To evaluate the safety and tolerability of PRAX-944 in participants with ET	
 • Incidence and severity of AEs • Changes in vital sign measurements • Changes in clinical laboratory results • Changes in ECG parameters • Incidence of C-SSRS measured suicidal ideation or behavior
Secondary	
To evaluate the efficacy of PRAX-944 on upper limb tremor in participants with ET	
 • Change from Baseline to Day 42 in TETRAS Upper Limb score (bilateral sum of items 4a, 4b, and 4c)
To evaluate the efficacy of PRAX-944 on other measures of tremor severity in participants with ET	
 • Change from Baseline to Day 7 and Day 21 in TETRAS Upper Limb score (bilateral sum of items 4a, 4b, and 4c) • Change from Baseline to Day 7, Day 21, and Day 42 in the following: 
 • TETRAS Performance subscale total score • Accelerometer-based upper limb score (bilateral sum of items 4a, 4b, and 4c) • TETRAS Performance individual item scores
To evaluate the efficacy of PRAX-944 on measures of disease impact in participants with ET	
 • Change from Baseline to Day 7, Day 21, and Day 42 in the following: 
 • TETRAS ADL subscale score • Quality of Life in Essential Tremor Questionnaire (QUEST) total and subscale scores
Exploratory	

	

2.2 Study Design

This multi-center clinical trial will assess the efficacy, safety, tolerability, and PK of PRAX-944 in participants aged 18 years or older who have had signs and symptoms consistent with ET for at least 3 years with onset before age 65. The clinical trial will be conducted in 2 parts (Part A and Part B).

- Part A of the clinical trial is open-label and will assess the safety and tolerability of PRAX-944, as well as the overall magnitude and pattern of change in ET severity. Daily dose levels will be titrated from 20 mg to 40 mg.
- Part B of the clinical trial consists of both an open-label titration phase and a randomized, double-blind, placebo-controlled withdrawal phase. Part B will assess the safety and tolerability of PRAX-944, as well as the overall magnitude and pattern of change in ET severity and the duration of that effect. Daily dose levels will be titrated from 20 mg to up to 120 mg during the open-label phase. In the randomized, double-blind, placebo-controlled withdrawal phase, participants will either be maintained on their final open-label dose or switched to placebo.

Both parts will consist of 3 periods: Screening/Baseline, Intervention, and Safety Follow-up.

Screening/Baseline Period

The Screening period for Part A and Part B will be up to 28 days (Day -28 to Day -1). Fourteen additional days (ie, 42 days total) will be allowed in the Screening period for participants who are discontinuing primidone.

Prior to any clinical trial procedures, participants will provide their consent to participate in the clinical trial. Screening assessments are as noted in the study Schedule of Activities (SoA; see [Appendix 1](#)).

Part A:

Following confirmation of eligibility, including review by the Sponsor or designee, participants will complete Baseline assessments (Day 0). Day 0 (Baseline) activities may be combined with Day 1 activities, provided that Baseline activities are completed before dosing and that dosing occurs in the morning of Day 1. Baseline efficacy assessments should either be conducted on Day 0 or Day 1 pre-dose.

Part B:

For participants in Part B, [REDACTED] will also be completed with accelerometry at Screening and via telehealth on Day -2 of the Screening period. Additional assessments added to Part B screening include [REDACTED]. Following confirmation of eligibility, including review by the Sponsor or designee, participants will complete Baseline assessments (Day 1). Some Baseline assessments (as indicated in SoA; see [Appendix 1](#)) may be completed on Day -1.

Intervention Period

Part A:

On Day 1, participants will receive a 20 mg dose of PRAX-944, administered in the morning. Participants will remain in a clinical setting under medical observation for approximately 6 hours. TETRAS performance assessments will be performed before dosing and 6 hours post-dose. After the first dose, participants will continue QAM dosing at home through Day 7. On Day 8, the dose will increase to 40 mg QAM from Day 8 to Day 14. Participants will return to the clinic on Day 14.

Safety and efficacy assessments will be obtained as described in the SoA (see [Appendix 1](#)). Participants who agree to optional additional PK sampling will remain overnight in the clinic on Day 1, Day 7, and Day 14.

Part B:

The open-label titration phase will begin on Day 1, participants will receive a 20 mg dose of PRAX-944 on an empty stomach. Participants will remain in a clinical setting under medical observation for approximately 6 hours. TETRAS Performance assessments will be performed before dosing and 6 hours (± 2) post-dose.

For dosing on Day 2 through Day 41, participants will be instructed to dose QAM at home. On Day 4, participants will escalate to 40 mg QAM through Day 7; on Day 8, participants should escalate to 60 mg QAM through Day 14; on Day 15, participants should escalate to 80 mg QAM through Day 21; on Day 22, participants should escalate to 100 mg QAM through Day 28; and on Day 29, participants will escalate to 120 mg QAM through Day 42, when they will return to the clinic for safety assessments and efficacy testing. On Day 41, participants will complete a TETRAS Performance Upper Limb assessment via a telehealth visit. Safety and efficacy assessments will be obtained during the open-label titration phase as indicated in the SoA (see [Appendix 1](#)).

[figure not shown]
If at any point during the open-label titration phase a participant does not tolerate escalation and the Investigator returns the participant to a lower dose level, the participant will continue according to the schedule outlined above, but no further dose changes will be allowed.

On Day 42, participants will complete the final clinic visit of the open-label titration phase. After Day 42, participants will begin the double-blind randomized withdrawal phase and either continue receiving PRAX-944 at their current dose or switch to placebo, depending on their randomization. Randomization in a 1:1 fashion may be completed at any time on Day 37 through 42. On Day 43 through Day 56, participants will take their assigned dose QAM and return to clinic on Day 56 for safety assessments and efficacy testing.

Safety Follow-up Period

Part A:

The Safety Follow-up period will take place from Day 15 to Day 21. At the end of the Safety Follow-up period, participants will return to the clinic on Day 21 for the final clinical trial assessments.

2.3 Determination of Sample Size

Up to 12 participants are planned to be administered PRAX-944 in Part A. Approximately 12 participants are planned to be administered PRAX-944 in Part B. Up to 12 additional participants may be enrolled at the discretion of the Sponsor to ensure inclusion of a broad range of tremor severity.

The sample size of each part is a convenience sample. The sample size was not selected according to any statistical power calculation. Instead, the sample size was determined according to feasibility and is thought to provide sufficient efficacy and safety data to inform the development of future controlled studies with PRAX-944 in participants with ET. In the open-label phases of the trial (Part A and Part B, open-label titration), a sample size of at least 10 participants would provide an 80% probability of observing at least 1 AE with an underlying incidence of 15% or greater. In addition, 10 participants should also provide approximately 80% power to detect an effect size of 1.0 on the primary endpoint of change from baseline in TETRAS Upper Limb score.

3 ANALYSIS SETS

An analysis data set will be created for efficacy, safety, and PK assessment. In addition to raw data values, each analysis data set will include derived variables as specified in [Section 4](#) (eg, baseline, total, and change from baseline values). All analysis data sets will also include key demographic information (including, but not limited to: study, center, subject identifier, age, gender, race, ethnic group, randomization number, analysis set eligibility flags, study treatment start and stop dates, reason for treatment discontinuation, randomized treatment [where applicable], and actual treatment received).

All data analyses will be performed using at least one of the below specified analysis sets. Participant eligibility for each analysis set will be finalized before database lock and unblinding of the data, where applicable.

3.1 Enrolled Analysis Set

The enrolled analysis set includes all participants who sign informed consent and are provided with an enrollment number. The enrolled analysis set will be used for all participant disposition analyses.

3.2 Safety Analysis Set

The safety analysis set includes all participants who received at least 1 dose of study drug. Participants will be classified according to actual treatment received. The safety analysis set will be used for all demographic, baseline characteristics, prior/concomitant medication, study drug exposure, and safety analyses.

3.3 Randomized Withdrawal Safety Analysis Set

The randomized withdrawal safety analysis set includes all participants who received at least 1 dose of blinded study drug in the randomized withdrawal phase of Part B. Participants will be classified according to actual treatment received. The randomized withdrawal safety analysis set will be used for all demographic, baseline characteristics, prior/concomitant medication, study drug exposure, and safety analyses for the randomized withdrawal phase of Part B.

3.4 Full Analysis Set

The full analysis set includes all participants who took at least 1 dose of study drug and have a valid baseline TETRAS assessment and at least 1 valid post-baseline TETRAS assessment. The full analysis set will be used for the analysis of all efficacy data, unless otherwise indicated.

3.5 Randomized Withdrawal Analysis Set

The randomized withdrawal analysis set is a subset of the full analysis set and includes all participants who were randomized into the double-blind, randomized withdrawal phase of Part B and have a valid Day 42 TETRAS assessment and at least 1 valid TETRAS assessment after Day 42. The randomized withdrawal analysis set will be used for the analysis of all efficacy data collected during the randomized withdrawal phase.

3.6 Pharmacokinetic Analysis Set

The pharmacokinetic (PK) analysis set includes all participants that received at least 1 dose of study drug and have sufficient PK concentration data for analysis. The PK Analysis set will be used for the descriptive statistical analysis of plasma concentrations and PK parameters.

4 DEFINITION OF STUDY VARIABLES

The following definitions will be used throughout the analysis plan for this study:

Study Day

Study day calculations (ex. study day of an event or a visit) will be defined as follows, assuming non-missing dates:

- Study Day = Date of event – Reference date + 1, when the date of interest occurs on or after the reference date;
- Study Day = Date of event – Reference date, when the date of interest occurs before the reference date;

If either date is missing, study day calculations will not be performed.

For this study, the reference date used will be the treatment start date. Based on the calculations above, there will be no study day zero.

Baseline and Change from Baseline

Unless otherwise specified, the baseline value is defined as the last non-missing value collected prior to receiving first dose of study drug. Values collected after the time of treatment start will be excluded from the calculation of baseline as applicable. Post-baseline values will be defined as those collected after the treatment start date (and time, as applicable).

Change from baseline will be defined as: assessment value – baseline value. Change from baseline values will only be derived for post-baseline assessments.

Randomization Baseline and Change from Randomization

The randomization baseline value, used as the reference value for double-blind randomized withdrawal phase efficacy endpoints, is defined as the Day 42 post-dose value. If the Day 42 post-dose value is unavailable, the randomization baseline value will be considered missing.

Change from randomization will be defined as: assessment value – randomization baseline value. Change from randomization values will only be derived for assessments conducted after the randomized treatment start date (and time, as applicable).

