4.10.2 Laboratory Test Results

Blood and urine samples will be collected by site staff for clinical laboratory testing. Urine pregnancy tests will be performed at the site and will be recorded in the eCRF as “Positive” or “Negative”. All other samples will be analyzed at the central laboratory. For all samples collected, the following data will be recorded in the eCRF: test category (ie, Chemistry, Hematology, Urinalysis, Coagulation, Pregnancy Test, Viral Serology or Urine Drug Screen), sample collection date, and sample time. For urine pregnancy tests, the result will also be recorded in the eCRF as “Positive” or “Negative”. An indicator for whether a repeat sample was taken (Yes/No) will also be recorded in the eCRF for each sample collected.

Collected laboratory samples will then be processed at the central laboratory for the calculation of reported values for the laboratory tests listed in [Appendix 3](#). Central laboratory data will include test category, lab test name, reported result, reported unit, reported reference range (ie, low and high), and abnormal indicator. Data from the central laboratory will be combined with the laboratory eCRF data prior to analysis.

Change from baseline values to each post-baseline assessment will be calculated for all continuous laboratory tests.

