4.10.3 Vital Sign Results

The following vital sign data will be recorded in the eCRF: assessment date, height, weight, BMI, as well as standing and supine temperature, pulse rate, respiratory rate, supine systolic blood pressure (BP), and diastolic BP. An indicator for whether a repeat assessment was taken (Yes/No) will also be recorded in the eCRF for each assessment.

Change from baseline values to each post-baseline assessment will be calculated for pulse rate, respiratory rate, systolic BP, and diastolic BP. In addition, potentially clinically important flags will be derived for systolic BP, diastolic BP, pulse rate, and respiratory rate (see [Table 1](#)).

Table 1: Potentially Clinically Important Criteria for Vital Sign Results

ECG measure	Lower PCI criterion	Upper PCI criterion
Pulse rate	≤50 bpm	≥130 bpm
Systolic BP	<90 mmHg	>130 mmHg
Diastolic BP	<50 mmHg	>85 mmHg
Change in systolic BP	decrease ≥30 mmHg	increase ≥30 mmHg
Change in diastolic BP	decrease ≥30 mmHg	increase ≥30 mmHg

BP = blood pressure; PCI = potentially clinically important

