5.8 Safety Analyses

For all safety variables, descriptive statistics will be presented by study part, treatment group, and visit (where applicable) using the safety analysis set and randomized withdrawal safety analysis set. In summaries of change from baseline safety variables, only participants with both baseline and change from baseline values will be included. No formal hypothesis testing will be performed for any safety variable.

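### In the Part B withdrawal phase, labs, vital signs and ECG are summarized only as change from the pre-drug value, so the change after randomization is not reported for these primary safety endpoints

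*SAP*

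**What the plan says.** SAP section 4 sets two reference values. Unless otherwise specified, "the baseline value is defined as the last non-missing value collected prior to receiving first dose of study drug"; in Part B that is a pre-drug value, about Day 1. The randomization baseline "is defined as the Day 42 post-dose value", and its stated use is as the value "used as the reference value for double-blind randomized withdrawal phase efficacy endpoints".

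The safety derivations use only the first of these. For laboratory data (SAP 4.10.2): "Change from baseline values to each post-baseline assessment will be calculated for all continuous laboratory tests". For vital signs (SAP 4.10.3), change from baseline "will be calculated for pulse rate, respiratory rate, systolic BP, and diastolic BP". SAP 4.10.4 does the same for ECG intervals. SAP 5.8.2 to 5.8.4 summarize reported values and change from baseline, and none of them mentions change from randomization.

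These summaries also serve the withdrawal phase. SAP 3.3 creates a set for "safety analyses for the randomized withdrawal phase of Part B", SAP 5.8 applies the safety summaries to it, and SAP 5 gives the columns as Placebo and PRAX-944. SAP 5.8 adds: "In summaries of change from baseline safety variables, only participants with both baseline and change from baseline values will be included". Day 42 laboratory tests, vital signs and ECG are scheduled in protocol Table 3. For Day 56, SAP 2.2 says that participants "return to clinic on Day 56 for safety assessments and efficacy testing".

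**The concern.** A withdrawal phase asks what happens when drug is stopped compared with when it is continued. For labs, vital signs and ECG, a Day 56 change from the pre-drug value spans 42 days on PRAX-944 in everyone and then 14 days of randomized treatment. A shift that arose on drug and persisted is printed as a change under Placebo. A shift that arose and fully reverted is printed as no change, the same figure as for a variable that never moved.

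The SAP does not treat its other data this way. Efficacy scores get change from randomization (SAP 4 and 5.7), and adverse events count as treatment-emergent for the withdrawal phase from the first randomized dose (SAP 4.10.1). Labs, vital signs and ECG stand beside adverse events as Part B primary endpoints, and this phase is the trial's only randomized safety evidence. No reason is given for leaving them on the pre-drug reference alone.

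**Working it through.** **Planning figures.** The only ones in the documents (SAP 2.3) do not depend on the safety reference. The chance of at least one event with n = 10 and incidence 15% is 1 - 0.85^10 = 0.803. Power for effect size 1.0 with n = 10 (paired t-test, two-sided 0.05 assumed) is also 0.803. Both match the stated 80%, and neither changes under the fix.

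**What each reference shows at Day 56.** Let d be the mean drug effect at Day 42, and f the fraction still present at Day 56 after 14 days of placebo. Assume the effect stays at d in those who continue drug.

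| | PRAX-944 | Placebo | Difference (PRAX-944 minus Placebo) |
|---|---|---|---|
| Change from pre-drug baseline | d | f·d | (1-f)·d |
| Change from Day 42 | 0 | -(1-f)·d | (1-f)·d |

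- f = 1 (persists): Placebo shows d from the pre-drug baseline and 0 from Day 42.
- f = 0.5: Placebo shows 0.5d and -0.5d.
- f = 0 (reverts): Placebo shows 0 and -d.

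The difference between arms is the same in every case. Randomized dosing starts on Day 43, so both reference values precede it and neither can be affected by the assigned treatment.

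**How much open-label effect can reach the Day 56 Placebo column.** Protocol 5.4.3 equates five half-lives with 3 days: 3 × 24 / 5 = 14.4 hours. From the last active dose on Day 42 to Day 56 is 14 × 24 = 336 hours, and 336 / 14.4 = 23.3 half-lives. Drug is essentially gone, so only effects that outlast exposure appear there.

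**Can the Day 42 to Day 56 change be recovered from the planned tables?** SAP 5 requires separate summaries by phase and puts open-label safety, other than adverse events, in one overall PRAX-944 column. SAP 5.7 adds open-label results to the withdrawal-set displays for efficacy; SAP 5.8 has no matching sentence. A table of Day 42 safety values by randomized arm is therefore possible but not guaranteed. Even with one, subtracting two means would not give the SD, median or range of the within-person change.

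**Threshold counts.** SAP Tables 1 and 2 flag changes of at least 30 mmHg in blood pressure and increases of at least 30 msec in QTcB and QTcF. By default these use the pre-drug reference. As an illustration only, assume a normal change with SD 10 to 15 (the same for either reference) and a persisting mean shift of 5 to 15 units. The chance that one assessment gives an upper flag against the pre-drug baseline is:
- lowest: 1 - Φ((30-5)/10) = 0.6%
- highest: 1 - Φ((30-15)/15) = 15.9%

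Against Day 42 with no further change, it is 1 - Φ(30/10) = 0.1% to 1 - Φ(30/15) = 2.3%. SAP 5.8.3 and 5.8.4 count such values at any time by treatment group and state no phase window. Open-label values could therefore be counted under Placebo unless the general by-phase rule of SAP 5 is applied.

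**The case against.** Several stronger readings are tempting, and the documents do not support them.

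- A reader might infer that the randomized comparison is biased. It is not: the expected difference between arms is (1-f)·d with either reference.
- A reader might infer that the Day 42 safety values go unused. They enter the by-visit summaries and the participant listings, and are unused only as a reference.
- A reader might infer that reversal or rebound cannot be seen. Side by side, d under PRAX-944 and 0 under Placebo does display a reversal, and overshoot past the pre-drug level appears as a change of opposite sign. The pre-drug reference shows overshoot more directly than Day 42 would, which is a reason to keep it.
- A reader might infer that all 42 days of drug effect sit in the Placebo column. After about 23 half-lives, only persisting effects do, and showing these against the pre-drug value is useful safety information.
- A reader might infer a gain in precision. With equal SDs, the ratio of the SD of change from Day 42 to that of change from Day 1 is √((1-ρ42)/(1-ρ1)), where each ρ is the correlation with Day 56. The documents give no correlations. With assumed ranges of 0.5 to 0.7 for Day 1 and 0.65 to 0.8 for Day 42, it runs from √(0.2/0.5) = 0.63 to √(0.35/0.3) = 1.08, which includes a loss.

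The sponsor can also say that the duration-of-effect objective quoted in SAP 7.1 covers tremor, disease impact, mood and global state but not safety, that no safety testing is planned, and that arms of about 6 to 12 can be read from listings. All of this is fair. It limits the point to interpretation, but it does not supply the missing summary. With descriptive output and no testing, the column values are what will be read.

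**Conclusion.** The point holds as a gap in reporting. For labs, vital signs and ECG in the withdrawal phase, the only planned change is from before the first open-label dose, and the within-person change after randomization is not summarized. At Day 56 the Placebo column reads f·d, where the change since randomization is -(1-f)·d; the two differ by the full Day 42 effect d, whatever the value of f. With 12 to 24 participants allocated 1:1 (about 6 to 12 per arm), change from Day 42 also subtracts any chance difference between arms in their Day 42 values.

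There is no bias in the randomized comparison, no planning figure changes, and no precision figure should be claimed. The algebra assumes a stable effect on continued drug. The washout figure takes the protocol's 3 days as exactly five half-lives. The flag percentages rest on assumed SDs and shifts. Day 56 collection is taken from SAP 2.2, because that part of the schedule is not fully visible. The change is worth making before database lock because it is nearly free and concerns primary endpoints.

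**What to change.** 1. In SAP 4, add a safety randomization baseline for labs, vital signs and ECG: the last non-missing value before the first randomized dose, normally Day 42. Do not carry over the post-dose condition from the efficacy definition, because the documents do not fix the timing of Day 42 safety assessments relative to the dose. Flag any participant whose value is not from Day 42.
2. In SAP 5.8.2 to 5.8.4, for the randomized withdrawal safety analysis set, report change from this value by arm beside change from the pre-drug baseline. Keep both, since each answers a different question.
3. In SAP 5.8.3 and 5.8.4, limit withdrawal-phase counts of potentially clinically important vital sign and ECG values to assessments after the first randomized dose.

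The cost is one derived variable, extra columns in existing tables and one sentence on the counting window. No new data, visits or participants are needed.
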